6.1.2. Analysis Methods

A summary will be provided for the following emergent adverse events per phase (Treatment phase, Follow-up phase) and for the combination of Treatment and Follow-up phase:

- any adverse events,
- serious adverse events,
- deaths due to AE,
- adverse events by toxicity grade,
- AEs at least possibly related to study medication,
- AEs for which study medication was permanently stopped,
- serious adverse events that were at least possibly related to study medication.

There will be no formal statistical testing.

Incidence tabulations will be provided for individual adverse events in the above categories (in case there are at least 5 events).

Listings will be provided for at least the following categories: all AEs, serious AEs, AEs leading to death, AEs leading to permanent stop, grade 3-5 AEs.

The summary, incidence tabulation for the individual preferred terms and subject listing will be provided for the RSV-related complications.

The following adverse events will be tabulated; or listed (in case there are less than 5 events) by subgroups (section 2.4): any AE, any RSV-related complications, any grade 3-5 AE, AEs that are at least possibly related to study medication, AEs leading to death, serious AEs, AEs leading to permanent stop of study medication.

6.2. Clinical Laboratory Tests

Laboratory parameters of hematology, serum chemistry and urinalysis will be investigated: All analyses will be done on SI-converted values as available in the database.

6.2.1. Definitions

Unifying multiple laboratory values by standardization:

Since local labs are used, the SI-converted values will be harmonized for selected parameters using the following formula and using the phantom laboratory generalized lab norms (GLN) as proposed by Francis Ruvuna, David Flores *et al.*^[4]

$$y = (x - L_i) * \frac{U_{cs} - L_{cs}}{U_i - L_i} + L_{cs}$$

Where

- y = the transformed individual analyte value to a common standard laboratory reference range;
- x = the original value;
- L_i and U_i = lower and upper limits of normal for individual laboratory analyte;
- L_{cs} and U_{cs} = lower and upper limit for the selected common standard laboratory or phantom laboratory GLN

The following additional rule applies for standard normal ranges with zero as lower limit and local normal ranges with non-zero lower limit. Zero will be used as lower local limit in the formula if the previous mentioned requirement was met.

The harmonized values, with the phantom laboratory GLN, will be used during the analysis.

Toxicity grades and abnormalities for laboratory parameters:

Toxicity grades will be computed according to the DMID adult toxicity grading list (see attachment at the end of this document) based on the harmonized values, for the parameters with harmonized values. In case different grades are available for fasted/non fasted results, the results are assumed to be taken in the condition as specified in the protocol (i.e. not necessarily according to possible remarks indicating a deviation to this). If no condition is specified in the protocol, the non-fasting gradings should be used.

In case no toxicity grades are defined for any laboratory test, then non-graded abnormalities (high/low vs. normal range) will be used instead.

The worst grade over the whole observational period (treatment phase, follow-up phase and combination of treatment and follow-up) will be determined.

Emergent definition for toxicity grades and abnormalities

An abnormality (toxicity grade or abnormality based on normal ranges) will be considered emergent in a particular phase if it is worse than the baseline value. If the baseline is missing, the abnormality is always considered as emergent. A shift from “abnormally low” at baseline to “abnormally high” post baseline (or vice versa) is also emergent. The emergent definition is applicable in both, the treatment and follow-up phase.

In case of missing date or time parts

Laboratory records with missing assessment date- or time-parts (any: day, month or year) will not be used in descriptive statistics, unless the scheduled target day or time is known and a unique phase allocation is possible taking this additional information into account. These assessments will be allocated to the correct phase using the available date (time) information, and the information on their assessment schedule. In case it is not possible to assign a unique phase (e.g. unscheduled time points), the assessment will be assigned to all possible active phases based on the available date and time information. These cases will be flagged in the respective listings.

Imputations of numerical values expressed as characters

In case a laboratory test result is *censored* (no numeric value is available, but only a verbatim term), the following rules are applied:

- ‘<x’ or ‘>x’: a numeric value will be imputed by a value exceeding the cut-off value with one unit
- ‘≤x’ or ‘≥x’: imputation by x.

This also applies to normal limits expressed as such.

No such imputations will be done for urinalysis parameters as these are usually character/categorical expressions.

Missing normal limits

Missing normal limits in the data base will be imputed at analysis level using the values specified and approved by the sponsor. This only applies if the missing normal limit is critical to determine a toxicity grade or an abnormality score, i.e. not for tests whose toxicity grade is based on the test value itself. Imputations, if applicable, will be flagged as applicable if shown in listings.

6.2.2. Analysis Methods

Actual values and change from baseline will be summarized by treatment group at each scheduled time point.

A cross-tabulation of the worst toxicity/abnormality versus baseline will be presented per phase (Treatment phase, Follow-up phase) and for the combination of Treatment and Follow-up phase. This table will also show the number and percentage of subjects per worst toxicity/abnormality, the number and percentage of subjects per emergent worst toxicity/abnormality and the cumulative number of subjects per emergent toxicity/abnormality or worse.

Mean \pm SE graphs over time for the actual values and changes from reference will be generated for all tests performed.

A listing of abnormal individual subject hematology and clinical chemistry values from scheduled and unscheduled time points will be provided. This listing will include all other time points for the corresponding subject/parameter, and will include both the original and harmonized values.

Grade 2 or higher toxicity laboratory values will be listed separately.

Urinalysis results will be listed. Proteinuria and urine WBCs will be summarized.

6.3. Vital Signs

Systolic and Diastolic blood pressure, heart rate, respiratory rate, body temperature and oxygen saturation (SpO₂) will be investigated.

6.3.1. Definitions

The vital signs abnormalities will be defined as indicated in [Attachment 2](#). In determining the abnormalities, the following rules are applied:

- worst grades/abnormalities are determined over the whole observational period for each trial phase separately, including post-baseline scheduled and unscheduled measurements of that phase.
- The abnormalities ‘abnormally low’ and ‘abnormally high’ /grades are considered equally important, i.e. if a subject has as well an abnormally low as an abnormally high or graded value post-baseline, both abnormalities are shown in the tables. (This means that the sum of the percentages can be more than 100%)

An abnormality will be considered emergent in a particular phase if it is worse than baseline. If baseline is missing, the abnormality is always considered as emergent. A shift from ‘abnormally low’ at baseline to ‘abnormally high’ post baseline (or vice versa) is also emergent.

Note: As described in section 2.1, for vital signs, means per analysis timepoint window will be calculated in order to have 1 assessment per analysis timepoint. These mean values per analysis timepoint will be used in the descriptive analyses over time. Abnormalities, to be used in the determination of the worst abnormality per phase, will not be determined on these mean values, but on the original records, including both scheduled and unscheduled assessments.

6.3.2. Analysis Methods

Actual values and change from baseline will be summarized by treatment group at each scheduled time point.

A cross-tabulation of the worst toxicity/abnormality versus baseline will be presented per phase (Treatment phase, Follow-up phase) and for the combination of Treatment and follow-up phase. This table will also show the number and percentage of subjects per worst toxicity/abnormality, the number and percentage of subjects per emergent worst toxicity/abnormality and the cumulative number of subjects per emergent toxicity/abnormality or worse.

Mean±SE graphs over time for the actual values and changes from baseline will be generated for all tests performed.

A listing of abnormal individual subject vital signs values will be provided. This listing will include all other time points for the corresponding subject/parameter.

6.4. Physical Examination Findings

Abnormal physical examination will be listed.

6.5. Electrocardiogram

PR, QT, QRS, QTc intervals and heart rate will be investigated. QTcF values will be used as reported, they will not be recalculated.

6.5.1. Definitions

The ECG abnormalities will be defined as indicated in [Attachment 3](#). In determining the abnormalities, the following rules are applied:

- Worst grades/abnormalities are determined over the whole observational period and for each trial phase separately, including post-baseline scheduled and unscheduled measurements of that phase.
- The abnormalities ‘abnormally low’ and ‘abnormally high’/grades are considered equally important, i.e. if a subject has as well an abnormally low as an abnormally high or graded value post-baseline, both abnormalities are shown in the tables. (This means that the sum of the percentages can be more than 100%)

An abnormality will be considered emergent in a particular phase if it is worse than baseline. If baseline is missing, the abnormality is always considered as emergent. A shift from ‘abnormally low’ at baseline to ‘abnormally high’ or ‘grade ...’ post baseline (or vice versa) is also emergent.

6.5.2. Analysis Methods

Actual values and change from baseline will be summarized by treatment group at each scheduled time point.

A cross-tabulation of the worst toxicity/abnormality versus baseline will be presented per phase (Treatment phase, Follow-up phase) and for the combination of Treatment and follow-up phase.

This table will also show the number and percentage of subjects per worst toxicity/abnormality, the number and percentage of subjects per emergent worst toxicity/abnormality and the cumulative number of subjects per emergent toxicity/abnormality or worse.

A tabulation of the worst QT/QTc change versus baseline per treatment per phase (Treatment phase, Follow-up phase) and for the combination of Treatment and follow-up phase will be presented

Mean \pm SE graphs over time for the actual values and changes from baseline will be generated for all tests performed.

A listing of abnormal individual subject ECG values will be provided. This listing will include all other time points for the corresponding subject/parameter.

7. VIROLOGY

7.1. Viral Strain Typing

The RSV subtype is determined at baseline using the RSV-A/B qRT-PCR assay performed at the central lab.

7.2. Viral Sequencing

Viral resistance will be evaluated by next-generation sequencing (NGS) of the RSV polymerase L-gene. Baseline samples from all subjects will be sequenced to identify pre-existing polymorphisms in their L gene. Post-baseline sequencing will be performed on the last evaluable on-treatment sample for all subjects to identify emerging amino acid substitutions in the L gene. Additional post-baseline sequencing can be performed on request of the sponsor virologist. Further validation of the RSV L-gene next generation sequencing assay is currently ongoing to determine the read frequency cut-off that will be used in the analyses.

7.2.1. Definitions

Virology results will be assigned to the visit windows as described in section 2.1 Visit Windows and Phase Definition. In addition to the time points corresponding to the visits at which samples for RSV L-gene sequencing are collected, the below time points will be considered:

- **Baseline (BL):** Time point with sequencing data available closest and prior to the first dose (ie the loading dose).
- **Sequence at End of Treatment (EOTSTPT):** Last available post-baseline time point during the treatment phase with sequencing data available
- **Sequence at End of Study (EOSSTPT):** Last available post-baseline time point in the study with sequencing data available
- **Entire post-baseline phase:** Aggregate of all available post-baseline time points in the study with sequencing data available

Genetic variations are defined as changes (on amino acid or nucleotide level) in the subject's virus's sequence compared to a reference sequence. Genetic variations can include substitutions, insertions and deletions. The reference sequences used will be RSV-A Long strain (GenBank Accession number AY911262) for RSV-A samples and RSV-B strain 9320 (GenBank Accession number AY353550) for RSV-B samples. Genetic variations will be reported on amino acid level.

- **Baseline polymorphism:** amino acid difference from the RSV-A or RSV-B reference strain detected at baseline above a certain read frequency cut-off.
- **Emerging genetic variation:** a genetic variation (amino acid substitution, insertion or deletion) that is absent (ie below the NGS read frequency cut-off) at baseline but present above a certain read frequency cut-off at a later post-baseline time point.

- **Enriched genetic variation:** a genetic variation (amino acid substitution, insertion or deletion) that is present at baseline and detected post-baseline with a minimum increase in read frequency compared to baseline.
- **Genetic variation profile:** a specific genetic variation or combination of genetic variations at one or more time points
- **RSV L-gene amino acid positions of interest:** The 4 L-gene positions of interest are 628, 789, 795 and 796 (based on in vitro selection experiments with Lumicitabine)

The read frequency cut-off that will be used for reporting RSV L-gene NGS data, as well as the read frequency cut-offs used in the definitions of baseline polymorphisms, emerging and enriched genetic variations are not yet defined but will be prior to the start of the analyses.

7.3. Analysis Methods

Baseline

The prevalence of baseline polymorphisms in the RSV L-gene, ie the number of subjects with baseline polymorphisms in the RSV L-gene, will be tabulated in frequency tabulation (n, %) by analysis time point and for the entire post-baseline phase. Amino acid changes from reference sequence at baseline will be listed for all subjects using the read frequency cut-off of the RSV L-gene NGS assay. Additionally frequency tabulations per time point and for the entire post-baseline phase will be made selecting only those baseline polymorphisms above a certain read frequency.

Similar tabulations will be made for the baseline polymorphisms on the positions of interest.

Post-baseline

Emerging and enriched genetic variations will be tabulated by analysis time point and for the entire post-baseline phase in frequency tabulations (n, %). Amino acid changes from reference sequence will be listed for all subjects with post-baseline sequencing data using the read frequency cut-off of the RSV L-gene NGS assay. Additionally frequency tabulations per time point and for the entire post-baseline phase will be made selecting only those emerging and enriched genetic variations above a certain read frequency.

Similar tabulations will be made for the emerging and enriched genetic variations on the positions of interest.

8. HEALTH ECONOMICS

Following medical resource utilization data will be explored.

8.1. Definitions

Measurement	Formula
Number of medical care encounters	
Medical care encounters, including surgeries and other selected procedures (inpatient and outpatient), as recorded on the eCRF.
 
The number of medical care encounters is derived as the frequency of the medical encounters other than those mandated in the protocol (eCRF).

Number of outpatient medical care encounters	
Similar to the description for number of medical care encounters, but only for outpatient medical care encounters, as recorded on the eCRF (Hospital Outpatient Department, Laboratory Department, Medical Practitioner Office, Home Care).

Duration of medical care encounter (days) per medical care encounter	
Duration of medical care encounter, is defined per medical encounter.
 
(End date of last medical care encounter – start date of first medical care encounter)+1.

Requirement for hospital readmission for respiratory reasons	
Does the subject require hospital readmission (ER, ICU, Hospice/Palliative Care Unit, Hospital Inpatient Department) for respiratory reasons after discharge? Categories will be Yes (1) or No (0).
 
Only derive this parameter for subjects that were discharged from hospital after first dose of study drug.

Requirement for hospital readmission for any reasons	
Similar as Requirement for hospital readmission for respiratory reasons

Duration of hospital readmission for respiratory reasons	
Duration of hospital readmission for respiratory reasons from discharge until end of the trial.
 
The duration of the readmissions can be calculated based on the start and end date of these medical readmissions. If more than 1 readmission took place, the duration can be calculated as the sum of the different durations.

Duration of hospital readmission for any	
Similar as Duration of hospital readmission for respiratory reasons

reason	
Hospital readmission for respiratory reasons	Medical review will be done immediately before data base lock on a list with unique coded adverse events (MedDRA Preferred Terms) for subjects who are re-admitted to the hospital to indicate which subjects were re-admitted for respiratory reasons

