9.6. Medical Resource Utilization and Health Economics

Medical resource utilization and health economics data, associated with medical encounters related to RSV and/or respiratory reasons, will be collected in the eCRF by the investigator and study-site personnel for all subjects at the timepoints specified in the [Time and Events Schedules](#).

Protocol-mandated procedures, tests, and encounters are excluded. The data collected may be used to conduct exploratory economic analyses and will include:

- Number and duration of medical care encounters, including surgeries and other selected procedures (inpatient and outpatient).
- Duration of hospitalization (total days length of stay, including duration by wards [eg, ICU]).
- Outpatient medical encounters and treatments (including physician or ER visits, tests and procedures, and medications).
- The number of subjects (proportion) who started antibiotic use after the first dose of the study drug up to the Day 28 follow-up visit.
- Requirement for, and duration of, hospital readmission for respiratory reasons from discharge up to the Day 28 follow-up visit.

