8.2. Analysis Methods

Descriptive statistics or frequency tabulations will be presented for all above parameters (except for the durations parameters) by treatment group.

A patient listing with details on the individual medical encounters will be created.

REFERENCES

2. Kliegman RM, Stanton B, St Geme J, Schor N, Behrman RE. *Nelson Textbook of Pediatrics*, 19th Edition.
3. Liptak, T. (1958). "On the combination of independent tests". *Magyar Tud. Akad. Mat. Kutato Int. Kozl.* 3: 171–197.

**ATTACHMENT 1. : LABORATORY: DIVISION OF MICROBIOLOGY AND
INFECTIOUS DISEASES (DMID) PEDIATRIC TOXICITY TABLES NOVEMBER 2007**

(Selected Values for children less than or equal to 3 months of age – does not apply to
preterm infants)

**For all parameters not listed in this table, please refer to
the DMID Toxicity Table for children >3 months of age**

HEMATOLOGY				
	Grade 1	Grade 2	Grade 3	Grade 4
Hemoglobin				
1-7 days old	13.0-14.0 g/dL	12.0-12.9 g/dL	<12 g/dL	Cardiac Failure secondary to Anemia
8-21 days old	12.0-13.0 g/dL	10.0-11.9 g/dL	<10.0 g/dL	Cardiac Failure secondary to Anemia
22-35 days old	9.5-10.5 g/dL	8.0-9.4 g/dL	<8.0 g/dL	Cardiac Failure secondary to Anemia
36-60 days old	8.5-9.4 g/dL	7.0-8.4 g/dL	<7.0 g/dL	Cardiac Failure secondary to Anemia
61-90 days old	9.0-9.9 g/dL	7.0-8.9 g/dL	<7.0 g/dL	Cardiac Failure secondary to Anemia
Absolute Neutrophil Count				
1 day old	5000-7000/mm ³	3000-4999/mm ³	1500-2999/mm ³	<1500/mm ³
2-6 days old	1750-2500/mm ³	1250-1749/mm ³	750-1249/mm ³	<750/mm ³
7-60 days old	1200-1800/mm ³	900-1199/mm ³	500-899/mm ³	<500/mm ³
61-90 days old	750-1200/mm ³	400-749/mm ³	250-399/mm ³	<250/mm ³

**DIVISION OF MICROBIOLOGY AND INFECTIOUS DISEASES (DMID)
PEDIATRIC TOXICITY TABLES NOVEMBER 2007**

(Selected values for children younger than or aged 3 months)

HEMATOLOGY (continued)				
	Grade 1	Grade 2	Grade 3	Grade 4
Bilirubin (fractionated bilirubin test must be performed when total bilirubin is elevated)				
<7 days old	-	20-25 mg/dL	26-30 mg/dL	>30 mg/dL
7-60 days old	1.1-1.9xN	2.0-2.9xN	3.0-7.5xN	>7.5xN
61-90 days old	1.1-1.9xN	2.0-2.9xN	3.0-7.5xN	>7.5xN
Creatinine				

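### SAP 8.1 labels encounter duration as per encounter but computes one span from the first encounter to the last, and SAP 8.2 leaves encounter and readmission durations out of the by-arm tables

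*SAP*

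**What the plan says.** SAP 8.1 has a row for the duration of medical care encounters in days. Its label and its first sentence both set the unit as the single encounter: "Duration of medical care encounter, is defined per medical encounter". The formula that follows is ("End date of last medical care encounter – start date of first medical care encounter)+1".

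Further down the same table, the row for respiratory readmissions uses a different rule for repeated events: "If more than 1 readmission took place, the duration can be calculated as the sum of the different durations". The row for readmissions of any cause follows it.

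SAP 8.2 sets the outputs: "Descriptive statistics or frequency tabulations will be presented for all above parameters (except for the durations parameters) by treatment group". It adds one further output: "A patient listing with details on the individual medical encounters will be created".

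Protocol 9.6 lists among the data to be collected "Number and duration of medical care encounters, including surgeries and other selected procedures (inpatient and outpatient") and "Requirement for, and duration of, hospital readmission for respiratory reasons from discharge up to the Day 28 follow-up visit". Protocol 11.7 plans a descriptive summary of resource utilization for each regimen and a comparison between regimens. It makes no exception for durations.

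**The concern.** There are two linked defects.

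First, the formula does not compute the variable that its label describes. A span from the first encounter to the last is one number per child, and it includes days on which the child received no care. Two programmers could reasonably derive different values from this cell, one following the label and the other the formula.

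Second, three variables are defined in 8.1 and then given no planned summary: encounter duration, readmission duration for respiratory reasons, and readmission duration for any reason. The protocol names the first two as data items and plans a by-regimen summary of resource utilization. The SAP gives no reason for the departure.

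At stake is the descriptive use of an exploratory endpoint. Without durations, the health-economics tables show how many encounters occurred and whether a child was readmitted, but not for how long.

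**Working it through.** The plan gives no numerical figure to reproduce. The check applies the SAP formula to assumed encounter dates and compares the result with the per-encounter definition. The documents give no encounter dates, so all dates below are assumptions within Days 1 to 28.

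**Formulas**

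- SAP 8.1 as written: span = end of last encounter − start of first encounter + 1.
- Per encounter, as labelled: end − start + 1 for each encounter.
- Gap counted as care (encounters that do not overlap): span − sum of the per-encounter durations.

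**Results**

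| Assumed encounters (study days) | SAP formula | Per encounter | Sum | Gap counted |
|---|---|---|---|---|
| Day 10 only | 10 − 10 + 1 = 1 | 1 | 1 | 0 |
| Days 10 and 11 | 11 − 10 + 1 = 2 | 1, 1 | 2 | 0 |
| Days 8 and 25 | 25 − 8 + 1 = 18 | 1, 1 | 2 | 16 |
| Days 10 and 24 | 24 − 10 + 1 = 15 | 1, 1 | 2 | 13 |
| Days 1–5 and 15–17 | 17 − 1 + 1 = 17 | 5, 3 | 8 | 9 |
| Days 8, 15–17 and 27 | 27 − 8 + 1 = 20 | 1, 3, 1 | 5 | 15 |
| Days 1 and 28 (extreme) | 28 − 1 + 1 = 28 | 1, 1 | 2 | 26 |

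With one encounter the formula agrees with the label. With adjacent encounters that do not overlap, it agrees with the sum but not with the individual durations. Once there is a gap, it exceeds both. For two 1-day visits within Days 1 to 28 the excess over the sum ranges from 0 to 26 days.

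A plain sum is not a safe per-child total either, because encounters include surgeries and procedures as well as admissions. Suppose an admission covers Days 15–17 and a procedure is recorded separately on Day 16. The sum is 3 + 1 = 4 days, but only 3 distinct calendar days are covered.

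**Coverage of the durations in Protocol 9.6**

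| Protocol 9.6 item | Where the SAP handles it |
|---|---|
| Duration of medical care encounters | Defined in 8.1, excluded from the by-arm summaries in 8.2 |
| Duration of respiratory readmission | Defined in 8.1, excluded from the by-arm summaries in 8.2 |
| Length of hospital stay | 5.3.1.3 and 5.3.2.3: Kaplan-Meier and accelerated failure time model |
| Duration of ICU stay | 5.3.1.3 and 5.3.2.3: descriptive analysis |

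The omission therefore concerns encounter and readmission durations only. Readmission duration for any reason, which the SAP adds in 8.1, is excluded in the same way.

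**The case against.** The strongest reply is that this is a wording slip without consequence. The cell states the per-encounter unit twice and only the formula line conflicts with it. The neighbouring readmission row sums separate stays, so counting gaps is not the SAP's general approach. Because 8.2 keeps durations out of the tables, no planned summary would carry an inflated value. The protocol calls these economic analyses exploratory and optional, and Protocol 11 leaves specific details to the SAP, so the exception in 8.2 could be a scoping choice.

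Much of this stands, and it limits the point. A reader might infer that the arm comparisons would be distorted by inflated durations. The documents do not support that: no by-arm table, test or estimate uses the encounter formula. A reader might also infer that gap-counting affects readmission durations; it does not, because that row has its own rule.

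Two things survive. A derivation that contradicts its own label still has to be resolved before anyone programs it. And Protocol 11.7 states the by-regimen summary without qualification, so leaving out variables that the SAP itself defines is a departure that needs either a reason or a correction. The SAP gives no reason.

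**Conclusion.** The point holds at low severity. As written, the encounter-duration formula conflicts with its per-encounter label and counts days between separate encounters as care: 18 days instead of 1 day each for 1-day visits on Days 8 and 25. The mechanism does not depend on those assumed dates, but its size does. How often it would arise cannot be judged from the documents, which give no encounter frequencies.

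Two broader readings are tempting and should not be taken. One is that every child with more than one encounter gets a wrong value. Two 1-day visits on the same day give the right per-encounter value, and adjacent encounters give the right total. The other is that the SAP drops all the durations the protocol asks for. Length of hospital stay and ICU duration are analyzed in SAP 5.3, while the number of encounters and the requirement for readmission are still tabulated by arm.

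As the SAP stands, the formula error can reach only derived data or listings. The primary endpoint, alpha and power are unaffected.

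**What to change.** Make both changes together. Lifting the exception in 8.2 alone would put the inflated spans into the tables.

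1. In SAP 8.1, define duration as end date − start date + 1 for each encounter. If a per-child total is wanted, define it as the number of distinct calendar days covered by that child's encounters, so that overlapping or same-day encounters are not counted twice.
2. In SAP 8.2, delete the parenthetical exception for durations, so that encounter and readmission durations are summarized descriptively by treatment group.

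The cost is a few lines of SAP text and a few more exploratory tables. No new data are needed, since the SAP already plans to list the individual encounters and derives readmission duration from recorded start and end dates.

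### SAP 8.1 counts ER visits under hospital readmission and omits them from outpatient encounters, contrary to Protocol 9.6

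*SAP*

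**What the plan says.** Protocol 9.6, with matching text in the synopsis, lists the resource-use data to be collected. One item is "Outpatient medical encounters and treatments (including physician or ER visits, tests and procedures, and medications". A separate item is "Requirement for, and duration of, hospital readmission for respiratory reasons from discharge up to the Day 28 follow-up visit"; it does not mention the ER.

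SAP 8.1 turns these items into variables:

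- Outpatient encounters are those in four settings: "Hospital Outpatient Department, Laboratory Department, Medical Practitioner Office, Home Care".
- Respiratory readmission is a Yes/No per subject, derived for children discharged after the first dose: "Does the subject require hospital readmission (ER, ICU, Hospice/Palliative Care Unit, Hospital Inpatient Department) for respiratory reasons after discharge".
- Readmission for any reason is defined as "Similar as Requirement for hospital readmission for respiratory reasons", so it takes the same list of settings.
- The overall count has no restriction by setting: "The number of medical care encounters is derived as the frequency of the medical encounters other than those mandated in the protocol (eCRF".

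On reporting, SAP 8.2 says "Descriptive statistics or frequency tabulations will be presented for all above parameters", by treatment group, with an exception for the duration variables, and adds a patient listing of individual encounters. SAP Section 1 says that the SAP is to be read together with the protocol. Neither document explains why the ER changes class.

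**The concern.** The two documents put the same event in different classes, and the SAP's classes are the ones that will be programmed. Protocol 3.2 gives lower use of hospital or outpatient services as the reason for collecting these data. The SAP moves ER visits across that hospital/outpatient divide.

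Readers are also likely to look at the readmission table next to length of stay, which is a modelled secondary endpoint, in a trial where children may go home after the Day 2 procedures. A table that mixes true readmissions with ER visits that ended in the child going home answers that question less clearly.

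**Working it through.** The plan states no rate or power for these variables, so there is no figure to reproduce. The check traces a single post-discharge respiratory ER visit through each set of definitions.

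| ER visit ends with | Definitions used | Outpatient encounters | Readmission |
|---|---|---|---|
| child sent home | Protocol 9.6 | +1 | No |
| child sent home | SAP 8.1 | 0 | can be Yes |
| child admitted | Protocol 9.6 | +1 for the ER visit, as listed | Yes |
| child admitted | SAP 8.1 | 0 | Yes |

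1. A child admitted from the ER is already a Yes through the inpatient or ICU entry. Listing ER among the readmission settings therefore changes the Yes/No result only for children who were not admitted.
2. The outpatient difference runs one way: SAP count = protocol-class count − number of ER visits. (If an ER visit that leads to admission is treated as part of that admission, the subtraction is the number of ER visits without admission.)
3. The readmission difference also runs one way. Let r be the proportion of discharged subjects with an inpatient return, and e the proportion whose only return was an ER visit without admission. The SAP proportion is at most r + e, where the protocol's classes give r. The ratio is at most 1 + e/r.
4. The overall encounter count includes ER visits wherever they are classed, so it does not change.

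Neither r nor e is in the documents. Purely as an assumption, take r = 3% to 5% and e = 5% to 10%. The SAP proportion would then run from 3% + 5% = 8% to 5% + 10% = 15%. The ratio would run from (5% + 5%)/5% = 2 to (3% + 10%)/3% = 4.3. With 60 children per arm, e would be 60 × 5% = 3 to 60 × 10% = 6 children, and r would be 60 × 3% = 1.8 to 60 × 5% = 3. With e = 0 the ratio is 1. These figures show how the result depends on e; they do not estimate it.

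**The case against.** **The protocol does not define hospital readmission.** It also speaks of admission to the ER when describing screening (Section 4), and inclusion criterion 2 accepts children who are in the ER. A sponsor could choose to count any acute return. This stands in part. The direct contradiction is the outpatient omission; the readmission problem follows from the protocol's classing of ER visits as outpatient. But both of those passages name the ER as an alternative to hospitalization, and for resource use Protocol 9.6 is specific.

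**Medical review may sort it out.** The last row of the SAP 8.1 table has coded adverse events reviewed to decide which re-admitted subjects returned for respiratory reasons. How a child seen in the ER and sent home would pass through that review is not stated, which is why the effect is put here as possible and not certain. The review separates respiratory from other reasons, not ER visits from admissions. It touches neither the any-reason variable nor the outpatient count.

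**The measures are exploratory, untested and defined alike in every arm, and a listing shows each encounter.** All true, and this limits the importance of the point. A listing does not correct the by-arm tables.

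Three stronger readings are tempting but not supported:

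- A reader might infer that the reported readmission rate will be several times too high. That rests entirely on assumed rates.
- A reader might infer that readmission durations will be misreported. SAP 8.2 leaves the duration variables out of its summaries.
- A reader might infer a conflict with the serious adverse event listing, because Protocol 12.3.2 makes rehospitalization for the same RSV disease a serious event. That rule is narrower than respiratory or any-reason readmission, and the same section exempts planned and social hospitalizations. The two counts could differ whichever way the ER is classed.

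**Conclusion.** The inconsistency is real and unexplained. Measured against the protocol's classes, the SAP's outpatient count is too low by the number of ER visits. Its two readmission proportions, respiratory and any-reason, can be too high by the subjects whose only return was an ER visit without admission.

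The direction follows from the definitions. The size cannot be derived from the documents and is zero if no such visits occur. The conclusion takes Protocol 9.6 as the reference classification and reads the SAP's list of settings literally.

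The consequence is confined to descriptive by-arm tabulations of exploratory variables. Primary and secondary efficacy analyses and total encounters are unaffected, and the duration variables are not summarized.

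**What to change.** Revise SAP 8.1 before database lock in one of two ways:

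- **Follow the protocol.** Remove ER from the readmission settings and keep Hospital Inpatient Department, ICU and Hospice/Palliative Care Unit, for both the respiratory and the any-reason variable. Count ER visits without admission as outpatient encounters. State the rule that links an ER visit to a following admission; the encounter dates that SAP 8.1 uses for its durations should be enough for this.
- **Report ER visits separately.** Tabulate them as their own category, outside both readmission and outpatient encounters, and state in the SAP that this departs from Protocol 9.6.

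Either way the cost is SAP wording and the matching programming. The SAP already names ER as a distinct setting, so no new data collection appears to be needed.
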